Genesis NICU is a Level II Regional Neonatology Center staffed full time by neonatologists from the University of Iowa Children's Hospital. The Genesis NICU provides family-centered treatment for babies born as early as 30 weeks gestation.

Participant Selection and Recruitment

The study will include 150 participants. There are no existing studies examining the time to diaper dermatitis for any treatment options (coconut oil or others), therefore, we conducted the simulation below to estimate a sample size that will have enough power to measure the primary outcomes in the study. The simulation generated time to discharge from a Gamma (3,2) and time to rash for coconut oil of Gamma (2,2) and standard Gamma (3,2). Patients that were discharged before getting diaper dermatitis were censored.

75 each Treatment: Gamma Scale 2 vs. 3, Shape = 2, p-value = 0.002.

The inclusion/exclusion criteria for the study is outlined below:

1. Inclusion criteria:
 - a. Babies admitted to the Genesis NICU
 - b. Anticipated stay in the NICU is ≥ 48 hours
 - c. Babies wearing diapers 24 hours a day
 - d. Parent willing to sign informed consent for the study
 - e. Parent willing to use the test products in the diaper area during the trial
 - f. Parent willing to not change the type or brand of diaper and wipes during the study
 - g. Parent willing to refrain from changing any other products whose use may have an effect of their baby's skin condition during the trial

2. Exclusion criteria:

- a. Babies with a gestational age <30 weeks
- b. Babies with major congenital malformations
- c. Active dermatological conditions other than diaper dermatitis that may affect trial results
- d. Known sensitivity to ingredients in trial products
- e. Babies whose parents have a hazelnut or coconut allergy
- f. Babies whose mother is <18 years of age
- g. Other severe acute medical conditions that may increase the risk associated with trial participation

3. Recruitment

[figure not shown]

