Expected	Any adverse event that is identified in nature, severity or frequency in the study protocol. Any adverse event that is previously known or anticipated to result from the underlying disease, disorder, or condition of the subject(s).
Unexpected	Any adverse event occurring in one or more subjects participating in the study, the nature, severity, or frequency of which is not consistent with either: 
 1. The known or foreseeable risks associated with the study procedures that are described in the protocol 2. The expected natural progression of any underlying disease, disorder, or condition of the subject(s) experiencing the adverse event and the subject's predisposing risk factor profile for the adverse event.

The Clinical Research Coordinator will assess adverse events on a weekly basis for this study by reviewing patient medical records. Serious adverse events will also be identified by nursing staff on the NICU and will be reported to the Clinical Research Coordinator. The Clinical Research Coordinator will report SAEs to [name] (Principal Investigator) to determine the need for additional treatment. Adverse events that meet the criteria outlined by the Genesis IRB (i.e., events that are unanticipated, serious or anticipated that occur with greater frequency or severity than expected) will be reported to the Genesis IRB within 10 working days after becoming aware of the information, as per Genesis IRB Standard Operating Procedures.

Data Analysis

Once data is transferred to the GHS Biostatistics Group, research team members will double enter the data and manage the databases, assign identification numbers to participants, perform edit diagnostics and prepare worksheets for analysis.

Comparative analyses of Coconut Oil and Standard of Care groups will include exact tests for comparing binomial characteristics, stochastic ordering for ordinal distributions (exact

permutation tests) and Wilcoxon rank sum tests for continuous factors. All will be analyzed with Cytel Studio StatXact Analyses.

Initially, data will be presented as a Kaplan-Meier plot of time to rash for the log-rank comparison of standard treatment and coconut oil. This will provide the probability of rash by treatment on any given day after the start of the study.

Cox proportional analyses will be used to control for risk factors to determine whether they are effect modifiers or confounders of the treatment effect.

Data Management

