## Introduction/Background

Diaper dermatitis is an inflammatory reaction of the skin in the perineal area of infants, and is a common pediatric condition. It can have many causes including infection (yeast, bacterial or viral), friction irritation, skin sensitivity to urine and/or feces, and allergies (perfumes). The overall incidence of diaper dermatitis in infants is estimated to be between 7% and 35%. Diaper dermatitis is often a result of increased moisture due to contact with urine and feces, followed by friction. Urine contact with diapered skin raises the skin pH, thus increasing skin permeability and activating fecal enzymes, which are known irritants that can cause skin breakdown. Skin breakdown encourages secondary skin infections that increases the challenge of managing diaper dermatitis. Diaper dermatitis can range in severity from generalized erythema (redness of the skin) to open wounds, and can cause significant pain for babies and distress for parents.

Premature infants have been found to be at higher risk for diaper dermatitis due to their age, and varying degrees of underdeveloped skin structures and functions. In addition, babies that are ill have a higher risk due to increased incidence of diarrhea, cancer, gastrointestinal anomalies, neurological disorders, genetic syndromes and malnutrition. Genesis Neonatal Intensive Care Unit (NICU) infants are often on a number of antibiotics that cause diarrhea, which significantly contributes to the challenges Genesis faces with diaper dermatitis. Genesis estimates its incidence of diaper dermatitis in the NICU is approximately 50%.

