## Participant Selection and Recruitment

The study will include 150 participants. There are no existing studies examining the time to diaper dermatitis for any treatment options (coconut oil or others), therefore, we conducted the simulation below to estimate a sample size that will have enough power to measure the primary outcomes in the study. The simulation generated time to discharge from a Gamma (3,2) and time to rash for coconut oil of Gamma (2,2) and standard Gamma (3,2). Patients that were discharged before getting diaper dermatitis were censored.

The inclusion/exclusion criteria for the study is outlined below:

1. Inclusion criteria:
  - a. Babies admitted to the Genesis NICU
  - b. Anticipated stay in the NICU is  $\geq 48$  hours
  - c. Babies wearing diapers 24 hours a day

- d. Parent willing to sign informed consent for the study
- e. Parent willing to use the test products in the diaper area during the trial
- f. Parent willing to not change the type or brand of diaper and wipes during the study
- g. Parent willing to refrain from changing any other products whose use may have an effect of their baby's skin condition during the trial

2. Exclusion criteria:

- a. Babies with a gestational age <30 weeks
- b. Babies with major congenital malformations
- c. Active dermatological conditions other than diaper dermatitis that may affect trial results
- d. Known sensitivity to ingredients in trial products
- e. Babies whose parents have a hazelnut or coconut allergy
- f. Other severe acute medical conditions that may increase the risk associated with trial participation

[figure not shown]
3. Recruitment

[figure not shown]
Participants will be recruited from the Genesis NICU. Each day the nursing staff will identify babies and parents that meet the inclusion/exclusion criteria. The nursing staff will notify the Genesis Clinical Research Coordinators (CRC) of eligible participants. The CRCs will also be screening the NICU patient lists to identify newly admitted babies. The CRC will approach the eligible participants to discuss the study and informed consent. The participants will have up to 24 hours to review the informed consent and decide whether or not to participate.

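### The simulation behind 75 babies per arm does not represent a benefit of coconut oil from the site's approximate 50% rash rate; with a benefit carried over at the same 1.5-fold ratio, about 64 events and 68% power are expected, against 86 events and 79% from the printed inputs

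*Protocol*

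**What the plan says.** Under Participant Selection and Recruitment, the protocol sets the size of the trial: "The study will include 150 participants". Because no earlier data on time to rash were found, a simulation was used to "estimate a sample size that will have enough power to measure the primary outcomes in the study". Its inputs are: "The simulation generated time to discharge from a Gamma (3,2) and time to rash for coconut oil of Gamma (2,2) and standard Gamma (3,2"). On censoring: "Patients that were discharged before getting diaper dermatitis were censored". The result printed in the protocol is: "75 each Treatment: Gamma Scale 2 vs. 3, Shape = 2, p-value = 0.002". The SAP section of the same name repeats the inputs and the purpose: "we conducted the simulation below to estimate a sample size that will have enough power to measure the primary outcomes in the study".

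Neither document gives a target power, a significance level, a sidedness or an expected number of events. The Data Analysis section names the test, a "Kaplan-Meier plot of time to rash for the log-rank comparison of standard treatment and coconut oil".

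The only local figure on rash frequency is in the SAP's Introduction/Background: "Genesis estimates its incidence of diaper dermatitis in the NICU is approximately 50" per cent. The protocol's Study Procedure says that standard care uses no product until a rash appears, so this figure is the natural starting value for the standard-care arm.

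**The concern.** Log-rank power depends on the size of the effect and on the number of events. The simulated run gets its event count from an arm with a rash rate well above the site's estimate, and as labelled that arm is coconut oil, the treatment meant to prevent rash. The trial asks whether coconut oil lowers rash from the usual level. Under that hypothesis both arms are at or below the usual level and fewer events occur.

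This is linked to the direction of the simulated effect, but correcting the direction does not settle it. The obvious repair, exchanging the two labels, keeps the 86 events and the 79% and moves the conflict to the standard-care arm. If the sizing statement is left as it is, a null result could be read as no benefit when the chance of missing a 1.5-fold delay was about one in three (under the assumptions below).

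**Working it through.** **Inputs**
- 75 per arm, common shape 2, scales 2 and 3 (protocol, result line). That line shows that the pairs read (scale, shape).
- Discharge: scale 3, shape 2. Standard-care rash: scale 3. Coconut oil rash: scale 2 (protocol and SAP).
- Rash censored at discharge; log-rank test (both documents).
- Standard-care rash of about 50% (SAP).
- Assumed, because not stated: two-sided 5%, and rash independent of discharge.
- Assumed: the size of the benefit. The plan gives only the contrast of 2 with 3.

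**Step 1. Rash before discharge.** For two independent gamma times of shape 2, with p = (discharge scale) / (discharge scale + rash scale),

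P(rash first) = 3p² − 2p³.

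With discharge scale 3:

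| Rash scale | p | P(rash first) |
|---|---|---|
| 2 | 3/5 = 0.600 | 1.080 − 0.432 = 64.8% |
| 3 | 3/6 = 0.500 | 0.750 − 0.250 = 50.0% |
| 4 | 3/7 = 0.429 | 0.551 − 0.157 = 39.4% |
| 4.5 | 3/7.5 = 0.400 | 0.480 − 0.128 = 35.2% |
| 5 | 3/8 = 0.375 | 0.422 − 0.105 = 31.6% |

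**Step 2. Expected events**
- Printed inputs, either labelling: 75 × 0.500 + 75 × 0.648 = 37.5 + 48.6 = 86.1.
- Standard care at 50% and any benefit: 37.5 + 75q with q < 0.5, so fewer than 75. This bound needs no effect size.
- Standard care scale 3, coconut oil 4.5 (ratio 1.5): 37.5 + 26.4 = 63.9.

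The ratio of 1.5 is a direct carry-over of 2 versus 3. It also keeps the absolute risk difference: 64.8 − 50.0 = 14.8 points and 50.0 − 35.2 = 14.8 points.

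**Step 3. Power by simulation** (up to 20,000 trials per scenario, two-sided 5% log-rank)

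| Standard care / coconut oil scale | Events | Power |
|---|---|---|
| 3 / 2 (printed) | 86 | 79% |
| 2 / 3 (labels swapped) | 86 | 79% |
| 3 / 4 | 67 | 42–43% |
| 3 / 4.5 | 64 | 68–69% |
| 3 / 5 | 61 | 85% |
| 2.3 / 3.45 (standard care about 60%) | 78 | 76% |

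Hand check: the mean log-rank Z is 2.75 for the printed run and 2.43 in absolute value for 3 / 4.5. Then Φ(2.75 − 1.96) = Φ(0.79) ≈ 79% and Φ(2.43 − 1.96) = Φ(0.47) ≈ 68%.

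Keeping rash scales 2 (standard care) and 3 (coconut oil) and moving discharge to scale 2 also gives standard care 50%. It yields the same 64 events and 68%.

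**Step 4. Sensitivity of the drop for ratio 1.5**
- Two-sided 5%: 78.8% to 68.0%, 10.7 points before rounding.
- One-sided 5%: 86.6% to 78.5%, 8.1 points.
- Times in whole days, two-sided: 77.8% to 68.5%, 9.3 points.

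**Step 5. The plan's own figure.** With the printed inputs the median p-value is 0.006, and about 37% of runs give 0.002 or less. The printed value is therefore a plausible single run, but it does not measure how often the trial would succeed.

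**The case against.** The strongest reply is that the assumed benefit, not the event count, decides the power. From scale 4 to scale 5 the events fall from 67 to 61 while power doubles from about 42% to 85%. The plan states no benefit, so the 10-point loss belongs to one chosen carry-over. This stands, and the figure should be quoted only with its range.

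A reader might infer that power falls under every reading of the gamma pairs. It does not. If the pairs are read as (shape, scale), the printed run gives 89 events and 93–94% power. Standard care (3,2) against coconut oil (4.5,2) then gives 58.5 events and 96–97%. The protocol's result line rules that reading out, but a claim about all readings would still be false.

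A reader might also infer that the trial cannot deliver 86 events. The documents do not support that. The 50% is approximate and covers the whole NICU. The trial enrols babies with an expected stay of at least 48 hours and logs pink or red skin at every diaper change, either of which could raise the recorded rate. At about 60% under standard care, a 1.5-fold delay gives 78 events and 76%, a loss of about 3 points. Nor does the general-infant range of 7% to 35% in the SAP introduction justify a more pessimistic case, because the same section gives the unit's own estimate.

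Finally, no power was promised as a number, so no stated figure is contradicted. That is correct. What remains is a claim of adequate power supported by a scenario other than the one under test.

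**Conclusion.** The point holds as an input mismatch in the sample size simulation, linked to the direction error. The printed inputs match the site's approximate 50% under standard care but make coconut oil worse. The swapped inputs make coconut oil better but put standard care at 65%. With standard care at 50% and any benefit, the expected total is below 75 events rather than 86.

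For a delay with the same 1.5-fold ratio, the expected figures are about 64 events and 68% power, roughly 10 points below the 79% implied by the printed inputs. The plausible range is 42–43% to 85% for scales 4 to 5, and about 76% if standard-care rash is nearer 60%. All powers rest on an assumed two-sided 5% test, independent discharge and the gamma shapes in the plan. The result does not show that 150 babies are too few for every benefit of interest; it shows that the plan has not demonstrated that they are enough.

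**What to change.** Keep N at 150. In Participant Selection and Recruitment of both documents:

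- rerun the simulation with a standard-care time to rash that gives about 50% rash before discharge (the printed scale 3, shape 2 already does) and a longer time to rash on coconut oil;
- state the significance level and sidedness;
- report expected events and power over repeated simulations for a range of benefits, for example about 64 events and 68% for a 1.5-fold delay, with scales 4 and 5 alongside, and one case with standard care near 60%;
- put these figures in place of the general claim of sufficient power and, in the protocol, of the single p-value.

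Merely exchanging the two labels is not a repair, because it assumes 65% rash under standard care.

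The cost is a short rerun and a few revised sentences in each document, with no extra babies and no change in procedures. The drawback is that the stated power becomes less favourable.

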Participants will be recruited from the Genesis NICU. Each day the nursing staff will identify babies and parents that meet the inclusion/exclusion criteria. The nursing staff will notify the Genesis Clinical Research Coordinators (CRC) of eligible participants. The CRCs will also be screening the NICU patient lists to identify newly admitted babies. The CRC will approach the eligible participants to discuss the study and informed consent. The participants will have up to 24 hours to review the informed consent and decide whether or not to participate.

Genesis estimates that approximately 200 – 250 babies are admitted to the NICU annually, which suggests that it is feasible to enroll 150 babies in approximately 1.5 years for this study. The estimated accrual rate is 8 babies per month. The research team will be reviewing the accrual rate on a monthly basis. If recruitment is slower than expected, the team will examine the reasons for slow recruitment and make adjustments, as needed. Any changes to recruitment procedures will be presented to the IRB before implementation.

Study Procedure

Participants that are eligible to participate in the study (those meeting the inclusion and exclusion criteria) will review and sign the study consent form. After consenting to participate the participants will be randomized into one of two groups.

The schema below illustrates how participants will be randomized.

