Participants meeting the inclusion/exclusion criteria that consent to participate in the study will be randomized to one of two Study Arms: Coconut Oil or Standard of Care. The Genesis Business Intelligence Unit will utilize block randomization (blocks of 5) to create 200 cards (50 extra to allow for potential participant attrition) that will include the randomized study arm and a randomly assigned patient number. These cards will be placed in a security envelope and stored in the Research office. Upon receipt of an informed consent, a Clinical Research Coordinator will draw an envelope in sequential order and will notify the participant's parents of his/her study arm. The Clinical Research Coordinator will also place the correct treatment (i.e., coconut oil or standard of care) in the participant's room and will notify the charge nurse in the NICU of the participant's study arm. The Clinical Research Coordinator will use a Randomization Log to record the participant's name, birthdate, study number, study arm and coordinator initials. This log will be kept confidential and secured throughout the study period in the locked Research office.

Participants in each arm will be cleaned with the same Pampers Sensitive brand wipes and will receive the same Pampers brand disposable diaper. The Coconut Oil group will receive coconut oil at each diaper change. An individual sterilized container of unrefined, organic coconut oil will be placed in the participant's room. The coconut oil will be obtained from a large jar and will be placed into the individual sterilized container at the time of randomization. The coconut oil will be labeled with the participant's name and date of birth. At each diaper change participants will

be cleaned with Pampers brand wipes and a generous layer of coconut oil will be applied to the diaper area, including buttocks and creases between thighs and hips. Participants in the Coconut Oil group that develop diaper dermatitis will continue to use coconut oil until they are discharged or reach the primary safety endpoint. They will also be switched from using Pampers Sensitive wipes to a dry washcloth and water, per the standard of care.

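### Both documents print one fixed block size of 5 and describe no blinding, so coordinators who enrol families could deduce about 10% to 17% of allocations in advance

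*Protocol*

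**What the plan says.** The randomization paragraph is the same in the protocol and the SAP (Study Procedure). The Business Intelligence Unit "will utilize block randomization (blocks of 5) to create 200 cards (50 extra to allow for potential participant attrition". The readable text gives no split within a block, no rule for balancing across blocks, and no variation in block size. It refers to a diagram ("The schema below illustrates how participants will be randomized"), which is not shown in the text available and may say more.

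The sample size statement in the protocol (Participant Selection and Recruitment) assumes equal arms: "75 each Treatment: Gamma Scale 2 vs. 3, Shape = 2, p-value = 0.002".

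On who knows what:
- Screening: "Each day the nursing staff will identify babies and parents that meet the inclusion/exclusion criteria". Coordinators also screen the NICU patient lists.
- Approach: "The CRC will approach the eligible participants to discuss the study and informed consent".
- Allocation: "Upon receipt of an informed consent, a Clinical Research Coordinator will draw an envelope in sequential order". The coordinator then tells the parents, places the product in the room, enters the arm in the Randomization Log, and "will notify the charge nurse in the NICU of the participant's study arm".

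The stated safeguards are a list made by a separate unit, security envelopes, a draw only after consent, randomly assigned patient numbers, and a log kept confidential in a locked office. Neither document describes blinding of parents, nurses, coordinators or those who record the rash.

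**The concern.** Envelopes hide the next card. They do not stop someone deducing it from the cards already opened. If the block size is known and past arms are visible, the end of a block can be worked out whenever one arm has used up its share. Here the size is printed in both documents, and the role that approaches families also draws the cards and keeps the record of past arms.

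What is at stake is selection. A coordinator who knows the next arm before approaching a family could, even without intending to, influence which baby receives it. There is some room for this. One exclusion criterion calls for judgement: "Other severe acute medical conditions that may increase the risk associated with trial participation". Expected accrual is 8 babies a month out of about 17 to 21 admissions (200/12 to 250/12), although the documents do not say how many of the rest would be ineligible or would decline. If babies at higher risk of rash were steered to one arm, time to rash would be affected directly, and the planned Cox model can adjust only for factors that were recorded.

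A second, smaller matter is that a complete block of 5 babies must split 3:2 or 2:3, so 75 per arm does not follow from the printed rule.

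**Working it through.** **The plan's own count.** 150 + 50 = 200 cards. That is 200/5 = 40 blocks of 5, and 150 babies fill 150/5 = 30 of them.

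**Reading A: a block is 5 babies, with the majority arm random.** There are 10 sequences with a 3:2 split and 10 with 2:3, all equally likely. The next arm is certain only once one arm has 3.
- In 2 of the 20 sequences one arm takes the first three places, so 2 allocations are certain.
- In 6 of the 20 the third baby of the majority arm falls in fourth place, so 1 allocation is certain.
- In the other 12 the block stands at 2:2 after four, so none is certain.

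Per block: (2×2 + 6×1)/20 = 0.5, and 0.5/5 = 10%. Over 30 blocks that is 15 babies. The best guess is right with probability 0.5, 0.6, 0.6, 0.7 and 0.7 at places 1 to 5, so 3.1/5 = 62%.

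**Reading B: 5 per arm, a block of 10.** For a known composition a:b, the certain share is [a/(b+1) + b/(a+1)]/(a+b). With 5:5 this is (5/6 + 5/6)/10 = 16.7%, or 25 of 150. Enumeration gives a best guess of 65.3%.

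**Conditional case: each block's majority arm is known beforehand** (3:2 fixed, or strictly alternating). (3/3 + 2/4)/5 = 30%, or 45 of 150, with a best guess of 72%. Neither document prints such a rule.

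**Pace.** At 8 babies a month, a block of 5 spans 5/8 of a month, about 19 days, which is easy to follow.

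**Arm sizes if a block is 5 babies.** With a random majority, one arm has 60 + Binomial(30, 0.5) babies. P(75:75) = C(30,15)/2^30 = 14%, and 70 to 80 per arm occurs in 96% of lists. Strict alternation gives 75:75. The same majority in every block, the extreme case, gives 90:60. Reading B gives 75:75.

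**Power cost.** The documents state neither alpha nor power, so assume two-sided 0.05 and a target of 80% or 90%. Relative information is e = 4ab/150², and power = Φ((1.96 + z)·√e − 1.96), where z is the normal quantile of the target power.
- 80:70: e = 22,400/22,500 = 0.996. Power is 79.8% or 89.9%, a loss of 0.2 or 0.1 points.
- 90:60: e = 21,600/22,500 = 0.960. Power is 78.4% or 88.8%, a loss of 1.6 or 1.2 points.

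**Alternatives compared.** For varying sizes the observer is assumed to know the set of sizes but not their order, with sizes equally likely (1,500 simulated lists of 150). The running-tally guess simply names the arm that is behind.

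| Scheme | Certain | Best guess | Running tally |
|---|---|---|---|
| 5 babies, random majority | 10% | 62% | 55% |
| 5 per arm | 17% | 65% | 65% |
| 5 babies, 3:2 known (not printed) | 30% | 72% | 67% (alternating) |
| Even sizes 4/6/8 | about 2% | 68% | 68% |
| Even sizes 8/10/12 | about 1% | 65% | 65% |

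The arm difference never exceeds half the largest block: 4 with 4/6/8, and 6 with 8/10/12 (at worst 78:72 at 150).

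**The case against.** The plan has real safeguards. The enrolling staff do not make the list, the cards are sealed, and the draw follows consent. The log is locked and patient numbers are random, so a number does not reveal its place in the sequence. Nurses would have to rebuild the enrolment order from what they see on the ward. Most eligibility criteria are objective, and two groups screen. All of this stands, and it makes the nursing route weak. It does not close the coordinator route, because that role draws each card and fills in the log.

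A reader might infer that up to 30% of allocations are predictable. The documents do not support that: the figure needs a fixed or alternating 3:2 rule that is not in the readable text and that the observer also knows. A reader might likewise infer 90:60 arms. That is only the extreme case, the diagram that is not shown may give a balancing rule, and the 5-per-arm reading removes the question. Nor do the documents show that enrolment would in fact be steered.

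It can also be said that varying the sizes exchanges one weakness for another, since a probable guess can be acted on as well as a certain one. This is partly right. With 4/6/8, guess accuracy is worse than under either reading of the printed words, which is why larger sizes are preferable.

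**Conclusion.** The point holds and should be fixed, as a preventable weakness rather than evidence of bias. On the two readings that the printed words allow, 10% or 17% of allocations can be known before a family is approached. This assumes that the observer knows the block size, tracks past arms from the start, and that each block is constrained to 3:2 or 2:3, or to 5:5. The exposure lies mainly with the coordinators. The documents give no basis for estimating how large any selection bias would be.

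The arm-size point is minor. The log-rank and Cox analyses remain valid with unequal arms, and the power loss is at most 1.6 points even at 90:60 under the assumed alpha and power. It calls only for the allocation ratio and block composition to be stated.

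**What to change.** In the Study Procedure section of both documents, before the cards are made, replace the block-size phrase with: *1:1 permuted blocks of randomly varying even size, generated by the Business Intelligence Unit, with block sizes held in a restricted document not available to enrolling staff*. The sizes themselves should not be printed in the protocol or SAP.

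Larger sizes are preferable. The set 8/10/12 serves as an illustration: certain allocations fall to about 1% (roughly 2 of 150) even if the set becomes known. It bounds the imbalance without guaranteeing 75:75.

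The cost is one sentence in each document and a list generated under the new rule. There is also a statistical cost. Best-guess accuracy with 8/10/12 is about 65%, which equals the 5-per-arm reading and is below the 72% of a known 3:2 split. It is, however, 3 points above random-majority blocks of 5, and 10 points above them for a simple running-tally guess (65% against 55%). Sizes 4/6/8 would hold the arms closer but raise guess accuracy to 68%.
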